#### **Insertion Site Pain or Discomfort – Relatedness Category**

1. Where is the location of the pain or discomfort?
  - If in the same location as the sensor on your skin, then Probably Related
  - If in a location where a sensor was within 2 days, then Possibly Related
  - If in a location where a sensor was 2+ days in the past, then Probably Not Related
  - If in a location where a sensor was never placed, then Not Related

### **Insertion Site Swelling – Severity Category**

1. On a scale of 1 to 10, where 1 is very little, and 10 is severe, how would you rate the amount of swelling?
  - If 1-5, do not record as AE
  - If 6-7, Mild AE
  - If 8-9, Moderate AE
  - If 10, Severe AE

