#### **CGM-based education and coaching**

This part of the study will be implemented by coaches who have undergone diabetes management training that incorporates device information, educational content, and techniques based on behavioral discussion and patient self-learning/empowerment. Coaches will also be equipped to help patients use activity data in conjunction with their CGM use. Coaches will receive training regarding human research subjects to insure the ethical treatment and safety of all participants. All training will be reinforced during contact with study staff.

The information contained in the Standard of Care document has been approved by the study's Medical Directors (co-investigators) as providing fundamental diabetes self-management information to patients with T2D. In the Standard of Care document, patients are instructed that this information does not replace individual guidance given to patients from their providers.

Each participant will be assigned a coach who will provide education and support by phone and secure text messaging. During weeks when patients are using the CGM system, they will be scheduled to receive a weekly phone call from their coach. Otherwise, patients can reach out to their coach by leaving a voicemail for the coach. Coaches will return calls within two business days. Education will be centered around the four educational objectives (food intake and PPG, walking to reduce PPG, medication adherence, and nighttime glucose monitoring) and reinforcement of messages in the patient standard of care document. The coach will provide education on how to optimally use the RT-CGM system for self-discovery, focusing on effective times to look at the RT-CGM and behaviors that are likely to impact the CGM (outlined above). Coaches will assist participants in setting personalized goals and act as a

sounding board for participants to discuss their self-discoveries. Coaches will review with patients the Rule of 15 to deal hypoglycemic episodes.

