### Risks of CGM

When the wire-like sensor is deployed by the applicator, participants can expect a sensation similar to a needle insertion for a blood draw. Risks of CGM use include discomfort during sensor insertion, along with pain, inflammation, redness, swelling, minor bleeding and minor infection at the sensor insertion site. Participants might also experience these symptoms as a result of contact between the adhesive pad of the sensor and the skin. In rare cases, an infection can spread to other parts of the body.

Allergic reactions can develop in response to the sensor, the adhesive, and other parts of the CGM. If these symptoms occur, participants have the ability to remove the CGM at will and can anticipate that their symptoms will clear up within one week.

The sensor and/or applicator may fracture during use. If a sensor remains in the skin, there is minimal risk to the patient as long as a physician confirms there are no symptoms of infection or inflammation.

Patients will be advised that the investigational sensor, transmitter, and smartphone must be removed before Magnetic Resonance Imaging (MRI), Computed Tomography (CT) scan, or diathermy treatment. The device is MR Unsafe. Participants should not bring any portion of the device into the MRI environment. The Dexcom IUO CGM System has not been tested during MRI or CT scans or with diathermy treatment. The magnetic fields and heat could damage the device, causing it to stop displaying glucose readings, display inaccurate glucose readings, or prevent alerts.

Patients will also be advised of CGM system warnings that may affect the proper operation of the device and/or the patient's safety. These warnings will be described in the informed consent and authorization form, and in the informational materials provided to patients when they receive their systems.

Patients will be provided with a phone number for Dexcom's Technical Support. Staff for this line will be well-qualified to address any potential questions and risks associated with the investigational device. Significant or serious health risks with CGM are not anticipated.

The same precautions have been taken to code and/or encrypt the investigational system's electronic data as have been taken with the commercial Dexcom devices. Regardless, throughout the program, patients will be advised not to rely on the device to make any treatment decisions, and to measure their blood glucose in order to confirm any symptoms of hypoglycemia.

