## 23. Appendix B

### Adverse Events Severity and Relatedness Questions

May 2017

When patients share a complaint, program coaches will identify the complaint in the Anticipated Complaints Guidebook. Based on the complaint type, coaches will then ask questions to determine:

1. Severity of the complaint (e.g., Mild, Moderate, or Severe), and
2. Relatedness of the complaint to the use of program devices (e.g., Not Related, Probably Not Related, Possibly Related, and Probably Related)

Coaches will document answers in the templates provided, including the Adverse Event document.

If the complaint falls in any of the severity categories highlighted in red, the coach will make a “warm transfer” to the study doctor and/or his staff so that the patient can be scheduled for an ancillary appointment.

If the complaint is an emergency, patients will be instructed to call 911.

If a patient has a complaint that is not listed in the Anticipated Complaints Guidebook, the coach can “warm transfer” the patient to the study clinic for guidance. The coach will document as much as possible in Adverse Event document. Follow up with the clinic will determine severity and relatedness.

Coaches will contact the PI when situations arise that are not covered in the Anticipated Complaints Guidebook.

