#### **Skin Itchiness – Severity Category**

1. On a scale of 1 to 10, where 1 is very little, and 10 is severe, how would you rate your skin itchiness?
  - If 1-5, do not record as AE
  - If 6-7, Mild AE
  - If 8-9, Moderate AE
  - If 10, Severe AE**

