### **Insertion Site Bruising – Severity Category**

1. On a scale of 1 to 10, where 1 is very little, and 10 is severe, how much bruising do you have?
  - If 1-5, do not record as AE, **unless the bruise is getting bigger, see question 2**
  - If 6-7, Mild AE
  - If 8-9, Moderate AE
  - If 10, Severe AE
2. Is the bruise or bump getting bigger?
  - If no, stop
  - If yes, **Moderate AE**
  - If yes and bruise is significantly getting bigger, **Severe AE**

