### **Insertion Site Infection – Severity Category**

1. Do you notice signs of infection that include inflammation, drainage, pus discharge and pain?
  - a. If no, then stop
  - b. If yes, on a scale of 1 to 10, where 1 is very little and 10 is severe, how much inflammation, drainage, pus discharge and pain do you have?
    - If 1 – 8, **Moderate AE**
    - If 9 – 10, **Severe AE**

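### Most Appendix B severity questions set no reference period and no re-rating step, so a skin reaction that has faded by the contact, or worsens after it, may be under-graded or not recorded as an AE

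*Combined protocol and SAP*

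**What the plan says.** Appendix B describes when the scripts are used: "When patients share a complaint, program coaches will identify the complaint in the Anticipated Complaints Guidebook". The coach then puts the severity questions for that complaint type.

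- **Swelling:** on a ten-point scale "where 1 is very little, and 10 is severe, how would you rate the amount of swelling". Scores of 1–5 are not recorded, 6–7 are mild, 8–9 moderate and 10 severe.
- **Itch:** "how would you rate your skin itchiness". The bands are the same.
- **Redness/rash:** the same bands, with follow-up questions on present itch and pain. A low redness score is still recorded if itch or pain is moderate.
- **Site pain:** one rating of how far pain affects daily activities. Scores of 1–2 are not recorded, 3–5 are mild, 6–8 moderate and 9–10 severe.
- **Bruising:** "how much bruising do you have", with the swelling bands. A second question upgrades a bruise that is still growing.
- **Infection:** if signs are present, "how much inflammation, drainage, pus discharge and pain do you have". Scores of 1–8 are moderate and 9–10 severe. If there are no signs, the script stops.
- **Bleeding:** graded by the size of the blood spot whether or not it has stopped.

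Section 6 (CGM-based education and coaching) says of patients using CGM that "they will be scheduled to receive a weekly phone call from their coach". It also says that patients may leave the coach a voicemail and that calls are returned within two business days. Section 9 defines pruritus, erythema and inflammation by their state 48 hours after removal.

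**The concern.** The redness, itch, pain and swelling scripts ask for no worst level since onset and no start or end date, and they do not tell the coach to rate the complaint again at a later call. Where a tense shows it is the present, so the natural reading is current status. The grade then depends on how many days separate the peak from the conversation as well as on how bad the reaction was. Fading pulls the grade down and can push it into the unrecorded band. A complaint rated 5 that later reaches 9 is rated again only if the participant raises it, and no rule says how two ratings combine.

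The counts and grades at stake belong to an investigational device. Section 9 commits the sponsor-investigator to report adverse events to the IRB, the manufacturer and the FDA. Section 10 says the study is meant to inform a larger one.

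**Working it through.** **Text check.** The plan states no figure to reproduce, so the first step is to set the scripts beside the other sections.

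1. The relatedness questions expect late reports: they distinguish a current sensor site, a site used within 2 days, and one used 2 or more days ago. The severity questions have no matching look-back.
2. The bleeding script grades an event that is already over. Redness, itch, pain and swelling do not get that treatment.
3. Section 9 fixes a time point (48 hours after removal). The Appendix B scripts carry none.
4. Bruising is exposed only once the bruise has stopped growing. Infection has no unrecorded band while signs are present, so the exposure there is a lower grade, or a stop once the signs have gone.

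**Illustration for swelling.** Inputs from the documents: the Appendix B bands and a 7-day call interval. Assumptions: the weekly call is the only contact; it falls uniformly 0–7 days after the peak; the participant rates the current state; the rating falls linearly from peak P to zero over T days and is rounded to a whole score.

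Rating at lag t = P(1 − t/T). It is recorded if it rounds to 6 or more, that is, if P(1 − t/T) ≥ 5.5. So:

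Pr(recorded) = (T/7)(1 − 5.5/P)

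For P = 8, T = 7: 1 − 5.5/8 = 0.3125, so 31% are recorded and 69% are not. The moderate grade is kept if the rating rounds to 8: 1 − 7.5/8 = 0.0625, or 6%. For P = 10 the severe grade is kept with probability (T/7)(1 − 9.5/10).

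| Peak (band at peak) | T (days) | Not recorded | Keeps peak band |
|---|---|---|---|
| 8 (moderate) | 7 | 69% | 6% |
| 8 (moderate) | 3.5 | 84% | 3% |
| 8 (moderate) | 2 | 91% | 2% |
| 10 (severe) | 7 | 55% | 5% |
| 10 (severe) | 3.5 | 78% | 3% |
| 10 (severe) | 2 | 87% | 1% |

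**Site pain** is less exposed because recording starts at 3 and severe at 9. For a peak of 8 and T = 7, 1 − 2.5/8 = 0.6875, so 69% are recorded and 31% are not. For a peak of 10, severe is kept in 1 − 8.5/10 = 15% (T = 7) or (3/7)(0.15) = 6% (T = 3).

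**A prompt voicemail.** Suppose the patient leaves a voicemail at the peak and is rated two days later. A swelling that peaked at 8 is then at 8 × 5/7 = 5.7 with a 7-day fade (rounds to 6, mild instead of moderate), or 8 × 1/3 = 2.7 with a 3-day fade (not recorded).

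**The case against.** The best reply is that the weekly call is only one of several routes. The scripts run on any complaint. Figure 2 makes the coach available by phone and text. Section 9 tells participants to call the clinical research coordinator, has the study doctor or staff assess severity, and sends manufacturer support reports to the coordinator. Later worsening can be graded at any such contact. This stands, and it is why the illustration is an upper end. It does not remove the point, because the documents set no reference period for those routes either.

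Some stronger readings are tempting, and the documents do not support them:

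- *Every Appendix B script takes a snapshot.* Bleeding does not, bruising asks about growth, and infection always records signs that are present. The swelling and itch questions are silent on time, so current status is an inference, though the natural one.
- *Most reactions will have passed by the weekly call, because Section 12 says participants* "can anticipate that their symptoms will clear up within one week". In context that sentence follows allergic reactions and the option to remove the device. It does not describe fading while a sensor is worn, and a sensor lasts 10 days.
- *Dates are never collected.* Answers go into an Adverse Event document and a Case Report Form that are not shown, and these may hold them.

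It is also fair that Section 10 plans no AE-rate analysis, so no planned result is affected, and that current severity is a defensible basis for triage. The redness exceptions also catch some reactions that a single score would miss.

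**Conclusion.** The gap is real for redness/rash, itch, site pain and swelling, and narrower for bruising and infection. Followed as written, the scripts allow a faded or later-worsening reaction to be under-graded or left out. A reader might infer that this will happen to most reactions. The documents support only that it may.

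The size cannot be derived from them. The 69% for a swelling that peaked at 8 rests on a sole weekly contact, a uniform lag, a linear 7-day fade and a participant who answers for today. A faster fade raises it. A report near the peak, or an answer given for the worst point, lowers it. The effect is confined to AE counts and grades. It is worth correcting because the device is investigational and the correction is cheap.

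**What to change.** In the Appendix B severity scripts for redness/rash, itch, site pain, swelling, bruising and infection:

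1. Ask for the rating at its worst since it began or since the last call, and keep today's rating as a second field.
2. Record start and end dates, if the Adverse Event document does not already do so.
3. Re-ask every open complaint at each later weekly call until it has resolved.
4. Use the worst rating as the recorded AE grade.
5. Leave the bands and the existing warm-transfer trigger unchanged, and have the sponsor state which of the two ratings the trigger uses. Otherwise a change meant for recording could alter transfers unnoticed.
6. Reconcile the scripts with the 48-hours-after-removal definitions in Section 9.

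The cost is template wording and a little extra time on calls that already take place. The downsides are some recall error and a higher reported AE rate. No sample size or primary measure changes.

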### **Insertion Site Swelling – Relatedness Category**

1. Where is the location of the swelling?
  - If in the same location as the sensor on your skin, then Probably Related
  - If in a location where a sensor was within 2 days, then Possibly Related
  - If in a location where a sensor was 2+ days in the past, then Probably Not Related
  - If in a location where a sensor was never placed, then Not Related

### **Insertion Site Bruising – Severity Category**

1. On a scale of 1 to 10, where 1 is very little, and 10 is severe, how much bruising do you have?
  - If 1-5, do not record as AE, **unless the bruise is getting bigger, see question 2**
  - If 6-7, Mild AE
  - If 8-9, Moderate AE
  - If 10, Severe AE
2. Is the bruise or bump getting bigger?
  - If no, stop
  - If yes, **Moderate AE**
  - If yes and bruise is significantly getting bigger, **Severe AE**

### **Insertion Site Bruising – Relatedness Category**

1. Where is the location of the pain or discomfort?
  - If in the same location as the sensor on your skin, then Probably Related
  - If in a location where a sensor was within 2 days, then Possibly Related
  - If in a location where a sensor was 2+ days in the past, then Probably Not Related
  - If in a location where a sensor was never placed, then Not Related

### **Insertion Site Bleeding – Severity Category**

1. Has the bleeding stopped?
  - If no, then: “Is the spot of blood greater than the size of a nickel?”
    - If no, then stop.
    - If yes, then **Severe AE**
  - If yes, then: “Is the spot of blood greater than the size of a nickel?”
    - If no, then stop.
    - If yes, then **Severe AE**

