#### [Integration with patient care](#)

Throughout the program, patients will be instructed to follow their normal care plan as directed by their physicians and as consistent with ADA 2017 standard-of-care guidelines. This includes taking medications as prescribed; engaging in physical activity—especially walking after meals; eating a diet that optimizes glucose control through food choice and timing; responding to hypoglycemia symptoms with a fingerstick and consuming a pre-determined amount of glucose; and monitoring emotional wellness. By providing a continuous graph of each participant's glucose, the CGM system illustrates how the above-described glucose management behaviors impact the participant's glucose.

Should patients in the course of the program experience any health problems associated with the use of their CGM devices, they will be directed to contact the study doctor's clinical research coordinator. The coordinator will assess the severity and relatedness of the event and arrange for appropriate care. Should patients mention a potential study-related health concern to their coach, the coach will actively work to assure the patient speaks with the study doctor, either through a warm transfer or callback.

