- None of the expected device-related adverse events as defined in the protocol and associated documents would be life-threatening or would result in any permanent impairment of a body function or permanent damage to a body structure;
- There are no expected electrical safety risks as the device has passed the electrical safety tests as per EN45502-1 and EN60601;
- If the subject feels any discomfort during the course of the study, he/she will be able to remove the device immediately (the device is not permanent);
- The device is being used to complement, not replace, self-monitoring of blood glucose meter information, and readings are not intended to be used alone to make diabetes self-management decisions. As with the currently approved device and per intended use of similar technologies, subjects in the study will be instructed not to use the device for diabetes therapy or management;

- Subjects will be instructed to monitor their blood glucose levels as per their usual practice.

Adverse events (AE) associated with the use of the device include pruritus (severe itchiness present 48 hours after removal), erythema (reddening of the skin present 48 hours after removal), and inflammation (swelling and pain, defined as 8 or greater on a 10 point scale 48 hours after removal) where the adhesive touches the skin; local infection at insertion site; and shooting pain located at the site of the sensor (defined as 8 or greater on a 10 point scale). Rarely, the sensor wire will fracture when the sensor is being inserted, worn, or removed. If a sensor breaks and no portion of it is visible above the skin, the participant will be instructed to not remove it and seek medical care from the study doctor and/or his staff.

No serious adverse events (SAE) or Unanticipated Problems (UP) are expected as a result of participation in this minimal risk study. However, AE, SAE and UP will be monitored in the following ways:

- Participants in the study will be instructed to call the study doctor's clinical research coordinator to report all AE, SAE and UP related to the use of the CGM devices. The study doctor and/or his staff will assess the severity of any health problems associated with the device, and if needed, see the patient at the study clinic to assure appropriate care.

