- Study coaches will listen for any reports of AE or SAE or UP in the course of their communications with participants, and will connect reporting patients with the study doctor's clinical research coordinator so events can be assessed and documented and patients can receive care, if needed.
- Any reports of AE or SAE or UP received by Dexcom's Technical Support representatives will be documented and reported to the Sponsor. Coaches will then promptly notify the study doctor's clinical research coordinator of these reports so that the coordinator can then follow up with the patient to assess event severity and relatedness, and schedule the patient for care, if needed.

The Sponsor-Investigator will receive CGM-related AE and SAE and UP information from Dexcom through secure data transfers. AE and SAE and UP information from the study doctor will also be stored and transferred securely. Any other records pertaining to AE and SAE from patient conversations with program staff will be recorded and documented using call-management software and the patient's Case Report Form.

The Sponsor-Investigator will ensure proper reporting of AE and SAE and UP to Chesapeake IRB, the CGM manufacturer, the FDA, and any other regulatory bodies according to regulations and standard operating procedures. (See Appendix C for a chart illustrating the reporting process, and Appendix B for AE assessment guidance for coaches.)

Patients will be provided with a summary printout of their recorded CGM data at the end of their participation with CGM. Patients can request a summary printout anytime during the trial. Patients can share their CGM data with their providers.

The Standard of Care guidelines associated with the program direct patients to seek medical care when needed. Guidance exists within the guidelines to seek medical advice when glucose values are extremely high over long periods of time, fluctuate rapidly from high levels to low levels and vice versa, or a

pattern of low glucose values is present. Coaches will remind patients of these guidelines but will not give medical advice. Coaches can send summary CGM data to patients upon patient request.

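### The coach's bleeding questions ask whether bleeding has stopped but never use the answer, so a small ongoing bleed gets no AE grade

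*Combined protocol and SAP*

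**What the plan says.** Appendix B gives coaches a short set of questions for each anticipated complaint, to set its severity and its relatedness to the devices. For insertion-site bleeding, the severity part opens by asking whether the bleeding has stopped. Each answer leads to the same follow-up, "Is the spot of blood greater than the size of a nickel". On both branches a no ends the questions and a yes gives a Severe AE.

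Other rules also bear on such a patient:

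- Appendix B, introduction: "Coaches will document answers in the templates provided, including the Adverse Event document". The transfer to the study doctor's office is conditional: "If the complaint falls in any of the severity categories highlighted in red". Also, "If the complaint is an emergency, patients will be instructed to call 911".
- Section 6, Integration with patient care: when a patient mentions a potential study-related health concern, "the coach will actively work to assure the patient speaks with the study doctor, either through a warm transfer or callback".
- Section 9: participants are told to call the study doctor's "clinical research coordinator to report all AE, SAE and UP related to the use of the CGM devices". Coaches who hear a report of an AE connect the patient with the "clinical research coordinator so events can be assessed and documented and patients can receive care, if needed".
- Section 12, Risks of CGM: the listed risks include "minor bleeding and minor infection at the sensor insertion site".

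**The concern.** A question whose two answers lead to identical branches does no work. The clinically natural reason to ask whether a bleed has stopped is to treat a continuing bleed differently, and these questions do not. A coach who follows only them would neither grade nor escalate a small bleed that is still going on.

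The neighbouring items suggest this was not intended. The bruising item does not record scores of 1 to 5, but overrides that floor when the bruise is growing, giving Moderate or Severe. The redness item overrides its floor when itch or pain is moderate. The bleeding item has no such override and can reach only two results, no grade or Severe, although the introduction to Appendix B describes a Mild, Moderate or Severe scale.

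What is at stake is the capture of a minor, expected device event and prompt referral of the few cases that persist. Participants are Medicare Advantage members. The exclusion criteria in Section 7 name neither bleeding disorders nor anticoagulant use, and they leave atrial fibrillation eligible. The documents do not say how many participants take anticoagulants, so the point is only that such patients are not screened out.

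**Working it through.** The plan states no figure to reproduce. The check is to list every path through the bleeding item and compare results.

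**Paths as written** (Appendix B, Insertion Site Bleeding – Severity Category)

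| Bleeding stopped? | Spot over nickel size? | Result |
|---|---|---|
| No | No | Stop, no grade |
| No | Yes | Severe AE |
| Yes | No | Stop, no grade |
| Yes | Yes | Severe AE |

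Hold size fixed and compare the two bleeding states:

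- Not over nickel size: stop versus stop, no difference.
- Over nickel size: Severe versus Severe, no difference.

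Bleeding status changes the result in 0 of 2 size strata. Of the two not-stopped paths, 1 of 2 ends with no AE grade.

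**Does the missing colour matter?** The transfer rule depends on severity categories marked in red, and the colour is lost in the text, so which categories trigger it cannot be confirmed. The ongoing small bleed reaches no severity category at all, so no colouring could trigger that transfer.

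**Paths after the proposed edit**

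| Bleeding stopped? | Spot over nickel size? | Result |
|---|---|---|
| No | No | AE, grade set by the medical directors |
| No | Yes | Severe AE |
| Yes | No | Stop, no grade |
| Yes | Yes | Severe AE, or lower if the medical directors so decide |

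Not-stopped paths with no grade: 0 of 2. Status then changes the result in 1 of 2 strata, or 2 of 2 if the grade for a large stopped bleed is lowered.

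**Exposure**

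- Wear period: 10 weeks × 7 = 70 days (Section 6, Recruitment).
- Sensor life: 10 days (Section 6, Program devices), so 70 / 10 = 7 sensors per participant. The payment schedule in Section 14 agrees: one first block plus $60 / $10 = 6 further blocks.
- Participants: 500 (Section 7), so 7 × 500 = 3,500 planned insertions at full wear.
- Share of insertions giving a small bleed still ongoing at a coach call: not in the documents. Assumed range 0.1% to 1%: 0.001 × 3,500 = 3.5 and 0.01 × 3,500 = 35 events.

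**The case against.** The strongest reply is that grading and referral are separate. The bleeding item sets a severity category, while Section 6 has the coach put any patient with a potential study-related health concern in touch with the study doctor, with no severity threshold. The coordinator then assesses severity and relatedness. On that reading a coach who follows the whole protocol still refers the patient, and all that remains is a surplus question. This largely stands as a limit on harm. It does not repair the item: none of these rules assigns a grade within it, and the Section 9 route for reported AEs may seem not to apply once the questions have ended without one.

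Second, leaving small events unrecorded is the appendix's usual design. Redness, itching, swelling and bruising scored 1 to 5, and pain scored 1 to 2, are not recorded, and nickel size may be the matching floor for bleeding. An ongoing spot no larger than a nickel could be ordinary oozing just after insertion. That is fair, and it is why a small stopped bleed should stay unrecorded. But if the floor is meant to apply whatever the status, the opening question is redundant and the item still needs an edit.

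Third, the event count is soft. The assumed rate has no anchor in the documents. Routine coach contact is a weekly call, so few small bleeds would still be running, and 35 looks generous. The 3,500 is nominal, because wear need not be continuous or use one sensor for the full 10 days. The conclusion does not rest on the count.

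Finally, the reporting chart in Appendix C and the Anticipated Complaints Guidebook cannot be seen. Certainty about the logic of the item therefore does not extend to what coaches would do in practice.

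**Conclusion.** The concern holds. As written, the answer on bleeding status has no effect on the grade, and an ongoing bleed not over nickel size leaves the item ungraded. This follows from the text alone and needs no assumption. The consequence is small: the status can still be noted in the coach's records, the general referral, self-report and emergency rules remain in force, minor bleeding is a disclosed risk, and no planned analysis is affected. The range of 3.5 to 35 events depends entirely on the assumed 0.1% to 1% rate and on full wear by 500 participants. This is a low-severity correction to a safety-capture rule, worth making because it is cheap.

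**What to change.** Edit only the branch for bleeding that has not stopped:

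- **Not over nickel size:** record an AE, with the grade set by the medical directors, and pass the patient to the study doctor's staff.
- **Over nickel size:** keep Severe.

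In the stopped branch, keep the stop for a spot not over nickel size. The medical directors should decide whether a stopped bleed over nickel size remains Severe.

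The cost is a one-branch edit to Appendix B, brief coach retraining, and the additional minor AE records and clinic transfers, which under the same assumption number 3.5 to 35 over the study.
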